#### Analysis

A formal statistical analysis plan, crafted by the study team in partnership with the statistical consultants, will be finalized prior to data analysis.

The primary outcome will be the score on the visual analog scale of pain in the PACU. Secondary outcomes reported will be the amount of opioid prescribed (in oral morphine equivalents) in the first thirty post operative days. Also reported will be the proportion of patients requiring narcotic pain medication, a composite of unplanned healthcare interactions within the first 30 post-operative days, PACU length of stay, nausea/vomiting, changes in cognition or coordination, and a composite of serious adverse events (ICU admission or death) within the 30 post-operative days.

Analyses will be performed in R. For the primary outcome, student's t-test will be used to compare the amount of opioid prescribed. For the secondary outcomes, either chi-squared or student's t-test will be performed to test for differences between those who received perioperative pregabalin and those who received placebo. For the secondary outcomes, multiple testing will be corrected using the Benjamini-Hochberg method [31].

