#### Secondary Hypotheses

We hypothesize that the use of the perioperative pregabalin in ureteroscopy with stent placement will:

- Have secondary benefits in the immediate post-operative period
- Decrease the proportion of patients receiving opioid prescription in the first 30 post-operative days
- Not decrease patient satisfaction with their procedure
- Not significantly increase the risk of adverse outcomes
- Decrease the risk of new persistent opioid use at 3, 6, and 12 months after surgery

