#### Secondary Endpoints:

Secondary endpoints include the following:

- Reported post anesthesia care unit (PACU) symptoms experienced
- Score on clock drawing test
- Number of unplanned contacts between the patient and the healthcare system within 30 days
- Reported satisfaction at 7- and 30-days post procedure
- Proportion of patients with new persistent opioid use at 3, 6, and 12 months after surgery

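### The protocol's Benjamini-Hochberg rule also covers the harm outcomes, where it makes a real increase harder to flag, and the SAP has no such rule

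*Protocol*

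**What the plan says.** The protocol's Analysis section names seven outcomes beyond the primary. The list opens with "Secondary outcomes reported will be the amount of opioid prescribed (in oral morphine equivalents) in the first thirty post operative days" and goes on to the proportion needing narcotics, unplanned healthcare interactions, PACU length of stay, and "nausea/vomiting, changes in cognition or coordination, and a composite of serious adverse events (ICU admission or death) within the 30 post-operative days". For these, "either chi-squared or student's t-test will be performed to test for differences between those who received perioperative pregabalin and those who received placebo". Then comes the multiplicity rule: "For the secondary outcomes, multiple testing will be corrected using the Benjamini-Hochberg method [31". No outcome is exempted and no false discovery rate level is given.

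The Secondary Endpoints section also holds harm measures: "Reported post anesthesia care unit (PACU) symptoms experienced" and "Score on clock drawing test". The section on outcome assessment says that adverse events will be captured by an optional nurse questionnaire in the PACU and by tracking unanticipated contact, so unplanned contact is partly a harm measure by the protocol's own account.

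Among the Secondary Hypotheses is that pregabalin will "Not significantly increase the risk of adverse outcomes". Another is that it will not lower satisfaction.

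The SAP compares the secondary outcomes by t-test or chi-square test and adds regression models for confounders. It mentions neither Benjamini-Hochberg nor any other correction, and neither document gives a margin or a confidence-interval criterion for safety.

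**The concern.** A multiplicity correction guards against false claims of an effect. That is the right protection for a claim of benefit, where significance supports the claim. For a safety hypothesis worded as the absence of a significant increase, the protection runs the other way: a larger p-value looks like support.

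What is at stake is false reassurance on the effects the protocol itself expects. Its Background and its Benefits and Risks sections both describe temporary changes in cognition and coordination as pregabalin's main side effects, and that outcome sits in the corrected list.

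**Working it through.** **1. The plan's own figure.** The SAP gives 59 per group for 80% power, with a difference of 1 VAS unit, SDs of 1 and 2.5, and two-sided alpha 0.05 (unequal-variance t-test). The standard error is √((1² + 2.5²)/59) = 0.3505, the noncentrality 1/0.3505 = 2.853, and the Satterthwaite df 76.1. Power is 80.4%, so the figure reproduces. With 40% dropout, 118/0.60 = 197, or about 200. I therefore use 59 per arm (the number the SAP powers for) and 100 per arm (no loss). The documents give no figure for the correction or for the safety hypothesis.

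**2. Direction.** Order the m p-values. Benjamini-Hochberg rejects up to the largest k with p(k) ≤ k·q/m. The adjusted value is p_adj(i) = min over j ≥ i of m·p(j)/j. Since m/j ≥ 1 and p(j) ≥ p(i), p_adj(i) ≥ p(i) always. This needs no assumption about rates.

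With m = 7 and q = 0.05 (assumed), the thresholds are 0.0071, 0.0143, 0.0214, 0.0286, 0.0357, 0.0429 and 0.05. Example: a harm p-value of 0.02 that is the smallest of seven becomes 0.02 × 7/1 = 0.14, unless other small p-values pull it down.

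**3. Size.** Assumptions:
- the seven outcomes of the Analysis section are treated as independent;
- one harm is truly raised, at assumed rates, and is tested by chi-square;
- ICU admission or death has p = 1;
- of the other five outcomes, none, two or four are real effects with 80% power each.

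Chance that the harm is flagged, by simulation:

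| Per arm | Harm rate | Uncorrected | Corrected, others null | Two others real | Four others real |
|---|---|---|---|---|---|
| 59 | 10% vs 30% | 80% | 52% | 64% | 71% |
| 59 | 10% vs 25% | 60% | 29% | 40% | 48% |
| 100 | 10% vs 25% | 82% | 56% | 67% | 74% |

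These figures move by about one point between runs. The loss is 26 to 31 points when all other outcomes are null and 8 to 12 points when four are real.

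Hand check of the second row, with power = Φ[(d − z·√(2p̄(1−p̄)/n)) / √((p₀(1−p₀)+p₁(1−p₁))/n)]. Here d = 0.15 and p̄ = 0.175; the null standard error is √(2 × 0.1444/59) = 0.0700 and the alternative one is √(0.2775/59) = 0.0686. At alpha 0.05 (z = 1.96): Φ(0.19) = 57%. At 0.05/7 (z = 2.69): Φ(−0.56) = 29%. Both agree closely with the simulation.

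**4. What remains without the correction.** By the same formula at 59 per arm and alpha 0.05, power is 33% for 10% vs 20% and 12% for 1% vs 3%.

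**The case against.** **The SAP may make the point moot.** The protocol says that a formal SAP will be finalised before analysis, and that SAP contains no correction. If it governs, the harm tests are already uncorrected and the loss does not occur. This stands as a limit. A reader might infer that the trial will certainly correct its harm outcomes; the documents do not support that. But nothing in the SAP withdraws the protocol's rule, so its use is unresolved.

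**No decision rule is stated.** A reader might also infer that the protocol declares non-significance to be proof of safety. It does not. That reading is only implied, by the wording of the hypothesis and the absence of any other criterion.

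**The size is soft.** Benjamini-Hochberg is adaptive, so the loss shrinks as other outcomes are rejected; the all-null column is close to a worst case. The harm rates come from no part of the documents. The count of seven is one reading: the Secondary Endpoints list differs and includes satisfaction and persistent opioid use. All this affects the size, not the direction.

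**The deeper fault lies elsewhere.** A non-significant difference test cannot show absence of harm, corrected or not, and step 4 of the working bears this out. That stands too: the correction aggravates this weakness but does not create it.

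**Conclusion.** The point holds for the protocol text. Its correction covers the harm outcomes and, if followed, can only make a harm signal harder to flag, while the safety hypothesis is worded so that the lack of a signal looks like support. That direction is certain.

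The size is conditional on the assumptions in the working: a loss of roughly 8 to 31 percentage points in the chance of flagging a real harm, over the scenarios shown. Whether any of it is incurred depends on which document governs, and on this they conflict. The primary analysis is unaffected. Exempting the harms removes an avoidable handicap; it would be wrong to infer that it makes the planned tests adequate to establish safety.

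**What to change.** In the protocol's Analysis section, confine Benjamini-Hochberg to the efficacy secondaries (opioid amount, proportion requiring narcotics, PACU length of stay), name the members of the family and state the false discovery rate level. State the same rule in the SAP, which now has none.

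Report nausea/vomiting, cognition/coordination (clock score), unplanned contacts, ICU admission or death, and satisfaction outside the family, as risk or mean differences with uncorrected 95% confidence intervals. Base the safety and satisfaction statements on those intervals, not on non-significance.

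The cost is wording in two documents, with no added patients, visits or data. The one downside is small: chance imbalances in harms will be flagged more often.

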#### **RESEARCH PARTICIPANT REGISTRATION AND RANDOMIZATION PROCEDURES**

#### Research Participant Registration

We will confirm eligibility as defined in the section entitled Criteria for Patient/Subject Eligibility.

We will obtain informed consent, by following procedures defined in section entitled Informed Consent Procedures.

#### Participant randomization

Randomization will be undertaken using the randomization module available in REDCap. Patients will be randomized to either "Group A" or "Group B". Medications will be distributed via the investigational pharmacy according to patient allotment. No one outside the investigational pharmacy will have knowledge of which group receives active medication.

#### DATA MANAGEMENT ISSUES

The research team will be responsible for project compliance, data collection, abstraction and entry, data reporting, IRB correspondence, problem resolution and prioritization and coordination of the protocol study team activities. The data collected for this study will be entered into a secure departmental server or will be stored online in the university approved resource, REDCap [32]. Source documentation and regulatory binders will be stored in a locked filing cabinet within a locked department office space. These sites are exclusively used for research documents and only members of the research team will have access to files for this study.

#### Quality Assurance

Routine data quality reports will be generated to assess missing data and inconsistencies. Accrual rates, and extent and accuracy of evaluations will be monitored throughout the study period. Potential problems will be brought to the attention of the study team for discussion and action.

#### Data and Safety Monitoring

The MU Health Care Data and Safety Monitoring Plans can be found online.

There are several different mechanisms by which clinical trials are monitored for data, safety and quality. There are institutional processes in place for quality assurance (e.g., protocol monitoring, compliance and data verification audits, therapeutic response and staff education on clinical research QA) and departmental procedures for quality control, plus institutional committees that are responsible for monitoring the activities of the clinical trials program.

#### **PROTECTION OF HUMAN SUBJECTS**

#### Benefits and Risks

The experimental intervention (perioperative pregabalin administration) is currently used at University of Missouri Hospital through the ERAS protocol. Numerous studies have shown significant patient benefits in all fields, including Urology. Several reviews have demonstrated the efficacy and safety of perioperative

gabapentinoid administration. The principal side effects of pregabalin are temporary cognition/coordination changes, with a very low risk of serious side effects. Therefore, we do not believe that the therapeutic aspects of this trial pose any serious risk different from patients undergoing ureteroscopy with stent placement under standard procedures.

#### Toxicities and side effects

Adverse outcomes are not anticipated with the regimen of pregabalin used in this study. Patients are closely monitored during the perioperative period and any serious events will be immediately brought to the attention of the study staff. All potential side effects will be recorded in questionnaires.

#### Alternatives / Therapeutic options

The alternative to participation in the trial would be to undergo ureteroscopy with stent placement according to the surgeon's standard practice and not to participate in the study. The patient may or may not receive pregabalin in this case. No other aspect of patient care would differ.

#### Financial Costs and Burdens

The cost of study drug and study drug administration will be covered by the study and will not be billed to the patients.

#### Patient incentives

The patients will be offered the following compensation:

Timing	Amount	Requirement
Day of surgery	\$5.00	Completion of day of surgery
		clock drawing test and visual
		analog scale
30 days post-op	\$5.00	Completion of early patient
		questionnaire

We may extend this to later time points pending future funding.

Monies will be supplied to patients in the form of e-gift certificates.

#### Privacy and Confidentiality

We will keep the study records confidential. No identifiers will be used in any reports or publications resulting from the study.

#### Volunteering Nature of the Study

Participation is entirely voluntary. All aspects of patient's care and monitoring will be unaffected by whether the patient chooses to consent for the study.

#### Serious Adverse Event (SAE) Reporting

Any SAE will be reported to the IRB as soon as possible, but no later than 5 calendar days. The reporting procedure will be followed as outlined in the University of Missouri protocol found in the "Core Standard Operating Procedure for Event Reporting.".

#### INFORMED CONSENT PROCEDURES

Before protocol-specified procedures are carried out, consenting professionals will explain full details of the protocol and study procedures as well as the risks involved to participants prior to their inclusion in the study. This may be performed by phone. Participants will also be informed that they are free to withdraw at any time. All participants will submit an electronically signed consent form. This consent form meets the requirements of the Code of Federal Regulations and the Institutional Review Board.

Before any protocol-specific procedures can be carried out, the consenting professional will fully explain the aspects of patient privacy concerning research specific information. In addition to signing the IRB

Informed consent, all patients must agree to the Research Authorization component of the informed consent form.

Each participant will sign the electronic consent form. The participant will receive a copy of the informed consent form. A member of the study staff will also sign the electronic consent form.

## APPENDICES

Appendix 1 – REDCap instruments

See instruments\_v1.0.pdf

Appendix 2 – Watson clock drawing form

See Watson\_v1.1.docx

Appendix 3 – Instructions for Watson clock drawing test

See Watson\_instructions\_v1.0.pdf

Appendix 4 – Visual analog scale

See VAS\_v1.1.docx

Appendix 5 – Post-op study specific instruction

See post-op\_instructions\_v1.0.pdf

Appendix 6 – Written consent and HIPAA authorization

See consent\_and\_hipaa\_v1.3.doc

Appendix 7 – E-consent

See econsent\_v1.0.pdf

Perioperative pregabalin as part of a multimodal treatment plan for pain after ureteroscopy with stent placement: a randomized, controlled trial

Statistical analysis plan

Version 1.0 Version date: February 27, 2020

Statistical Analysis Plan

Enrolled subjects' characteristics will be summarized using mean \pm SD for continuous variables and proportions for categorical variables. The primary outcome of interest, the value on the visual analog scale of pain score (VAS score), will be summarized overall and by treatment group, those who received perioperative pregabalin and those who received placebo. To examine the research question, an independent sample t-test will be conducted to assess if differences exist on VAS scores by the treatment group. The assumptions of normality and homogeneity of variance will be assessed. Normality of the scores will be assessed using the One-Sample Kolmogorov-Smirnov test. Homogeneity of variance will be assessed using Levene's Test for the Equality of Error Variances. The *t*-test will be two- tailed with the probability of rejecting the null hypothesis when it is true set at *p* < 0.05. If groups are unbalanced with respect to one or more patients' characteristics, we will perform a stratified analysis of VAS scores based on that characteristics.

For the secondary outcomes of interest, a two sample t-test or a Chi-square test of independency will be used to compare the treatment groups for continuous and categorical outcomes, respectively. In addition to univariate analysis, we will fit a generalized linear model or logistic regression model of outcome on treatment group controlling for possible confounding variables such as, gender, age, pre-operation VAS score and pre-operation Watson clock drawing score, depending on type of outcome.

Power Analysis

Group sample sizes of 59 per group achieve 80% power to reject the null hypothesis of equal means when the population mean difference in VAS score is as little as 1 unit, assuming the standard deviations of 1 for group 1 (based on our pilot study) and 2.5 for group 2 (from literature), and with a significance level (alpha) of 0.05 using a two-sided two-sample unequal-variance t-test. Assumption about 40% dropout rate, it requires approximately 200 total subjects with a planned 1:1 placebo to active treatment enrollment ratio. We estimate at least 500 eligible procedures are conducted each year at our institution. Accounting for excluded patients and those who do not wish to participate, we estimate that full enrollment should be attainable within one year.

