#### Primary Endpoints

The primary endpoint will be the value on the visual analog scale of pain score supplied by the patient approximately one hour after reaching the post-operative area.

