#### Subject Inclusion

- Age  $\geq$  18 years
- Undergoing ureteroscopy with plan for stent placement

Subject Exclusion

- Renal insufficiency (eGFR < 50 mL/minute/1.73 m^2)
- Ureteral stent in place >30 days
- Chronic opioid use
- History of opioid abuse

- Chronic gabapentinoid use
- History of gabapentinoid abuse
- Plan for inpatient hospitalization either leading up to or after treatment
- Pregnancy
- Inability of the patient to consent for themselves in English
- Allergy to gabapentinoid
- Liver failure or hepatic dysfunction
- No email address that is regularly checked

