### **EVALUATION DURING TREATMENT/INTERVENTION**

#### Not part of usual care

This protocol requires several evaluations outside those typically used. These are all questionnaires.

Timing	Questionnaire	Respondent
Before day of surgery OR on day of surgery	Screening questionnaire	Study staff
	Baseline questionnaire and demographic information	Patient
	E-consent	Patient
	Preop Watson clock drawing test and visual analog scale of pain	Patient
Day of surgery	PACU	Study staff
	Watson clock drawing test and visual analog scale of pain \$	Patient
3 days post op	Early patient questionnaire	Patient
7 days post op	Early patient questionnaire	Patient
30 days post op	30 days post op chart review	Study staff
	Early patient questionnaire \$	Patient
90 days post op	Late patient questionnaire	Patient
6 months post op	Late patient questionnaire	Patient
1-year post op	Late patient questionnaire	Patient
	1-year post op chart review	Study staff
Untimed	Unanticipated contact	Study staff/Treatment staff
	Evaluation of trial	Patient

\$ indicates questionnaires for which compensation will be provided. Please see details of compensation.

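### The primary PACU pain comparison is an unadjusted t-test although a pre-op VAS is already scheduled; prespecifying adjustment for it would buy modest precision at almost no cost

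*SAP*

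**What the plan says.** The Protocol (Primary Endpoints) defines the primary outcome as the "visual analog scale of pain score supplied by the patient approximately one hour after reaching the post-operative area". For it the SAP (Statistical Analysis Plan) states: "To examine the research question, an independent sample t-test will be conducted to assess if differences exist on VAS scores by the treatment group". No covariate enters that test.

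The Protocol's table of evaluations outside usual care lists "Preop Watson clock drawing test and visual analog scale of pain", completed by the patient, with the timing given as "Before day of surgery OR on day of surgery". A pain score of the same kind is therefore due to be collected before the outcome.

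The SAP does mention this score as a covariate. The paragraph opens "For the secondary outcomes of interest, a two sample t-test or a Chi-square test of independency will be used" and goes on to add a generalized linear or logistic model "controlling for possible confounding variables such as, gender, age, pre-operation VAS score and pre-operation Watson clock drawing score, depending on type of outcome". Its position points to the secondary outcomes. The closing words allow a wider reading, but even then the model comes on top of the univariate tests, its covariate list is open, and it is not named as primary.

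The only covariate provision clearly attached to the primary outcome is conditional. If patient characteristics turn out unbalanced, "we will perform a stratified analysis of VAS scores based on that characteristics". Imbalance, the strata and the way strata would be combined are not defined.

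**The concern.** If pain before surgery predicts pain in the PACU, a model that includes it removes part of the outcome's variance and gives a narrower interval for the same treatment effect. Here the score is scheduled anyway, so leaving it out of the primary analysis gives up precision for nothing.

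How well it predicts is unknown. Among stented patients the Protocol excludes only those with "Ureteral stent in place >30 days", so patients with and without a stent can enter and pre-op pain may well vary between them. That is inference, not a documented fact.

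The size of the benefit also depends on how many patients supply a PACU VAS. The SAP plans for 59 per group after 40% dropout. A score taken about an hour after arrival may be obtained from many more than that, in which case power is already high and adjustment adds fewer points. The proportional narrowing of the interval is the same at any sample size.

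**Working it through.** **Inputs.** From the SAP (Power Analysis): difference 1 VAS unit, SDs 1 and 2.5, two-sided alpha 0.05, unequal-variance t-test, 59 per group, 40% dropout, about 200 in total. Assumed, because the documents are silent: r between pre-op and PACU VAS of 0.2 to 0.5, equal in both arms, with complete pre-op VAS unless stated.

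**1. The plan's own figure.** SE = √((1² + 2.5²)/59) = √(7.25/59) = 0.351, so the noncentrality is 1/0.351 = 2.85. Satterthwaite df = 58 × 7.25²/(1² + 6.25²) = 76.1. Noncentral-t power is 80.4% (58 per group gives 79.7%). Inflation: 118/0.60 = 197, about 200. The plan's sample size is reproduced.

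**2. Variance after adjustment.** One model with a common slope on standardised pre-op VAS fits, with equal groups, b = (r×1 + r×2.5)/2 = 1.75r. The residual variance in an arm with SD s is s² − 2brs + b²:

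- SD 1 arm: 1 − 3.5r² + 3.0625r² = 1 − 0.4375r²
- SD 2.5 arm: 6.25 − 8.75r² + 3.0625r² = 6.25 − 5.6875r²
- Sum: 7.25 − 6.125r², which is 7.25 × (1 − 0.845r²)

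The ratio of interval widths is √(1 − 0.845r²).

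**3. Results** (noncentral-t power with these variances):

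| r | Interval width ratio | Power, 59 per group | Power, 80 per group | Power, 100 per group |
|---|---|---|---|---|
| 0 | 1.000 | 80.4% | 90.8% | 95.8% |
| 0.2 | 0.983 | 81.7% | 91.7% | 96.3% |
| 0.3 | 0.961 | 83.4% | 92.8% | 97.0% |
| 0.4 | 0.930 | 85.8% | 94.3% | 97.7% |
| 0.5 | 0.888 | 88.7% | 96.0% | 98.6% |

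**4. Simulation of the model actually recommended** (linear model with HC3 standard errors, normal data, 40,000 trials per cell). At 59 per group, power is 80.1%, 80.9%, 82.6% and 88.1% for r = 0, 0.2, 0.3 and 0.5, against 80.3% to 80.7% for the unequal-variance t-test in the same data. At r = 0.3 it is 92.8% with 80 per group and 96.8% with 100. The formula in steps 2 and 3 is therefore slightly optimistic at 59 per group.

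**5. Less favourable conditions** (59 per group, r = 0.3).

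- Pre-op VAS missing completely at random and set to the overall mean: the variance sum is (1 − m)×6.70 + m×7.25 for missing fraction m. Power is 82.8% at m = 0.2 and 82.2% at m = 0.4 by formula, and 81.9% and 81.5% by HC3 simulation.
- Correlation in one arm only: the formula gives 82.0% if it is the SD 2.5 arm and 80.6% if it is the SD 1 arm. HC3 simulation gives about 81% and 80%, which is little or no gain.

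**6. Why the standard errors must allow unequal variances.** With the SAP's SDs, no true difference, and an illustrative split of 50 and 68 completers, a pooled t-test has type I error of about 3% (50 in the SD 1 arm) or 8% (68 in the SD 1 arm). The unequal-variance t-test and the HC3 model stay between 4.7% and 5.1%.

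**The case against.** The strongest reply is that nothing here is wrong. An unadjusted comparison in a randomised trial is unbiased, the trial was powered for exactly that, and the figure reproduces. The SAP also names pre-op VAS as a covariate, under wording that could be read to reach the primary outcome. The benefit rests on a correlation that no document gives. It could be low, because pre-op pain may be recorded before the day of surgery, whereas PACU pain follows anaesthesia, ureteroscopy and stent placement. At r = 0.2, or with correlation in one arm only, the recommended model gains about half a point or nothing. With 100 per group and r = 0.3 the gain is about one point. The change also brings a robust-variance choice, a baseline definition and a rule for missing values.

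Most of this stands, and it fixes the weight of the point: this is an optional improvement. It does not remove the point. On either reading of the SAP, the adjusted model is neither fixed nor designated primary, so covariates could be chosen after the results are seen. The downside is bounded at about one point of power, while the upside at the planned 59 per group is roughly 8 points at r = 0.5. The added rules can be stated in a few sentences.

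**Conclusion.** The point holds as a suggestion worth considering. The primary test, as written, does not use a baseline score that the trial already plans to collect. Adjusting for it would narrow the interval by about 2%, 4%, 7% or 11% at r = 0.2, 0.3, 0.4 or 0.5. At r = 0.3 the power gain is about 3, 2 or 1 points with 59, 80 or 100 per group, and simulation of the robust model puts the first of these slightly lower. At r = 0 the cost is up to about 1 point. These figures assume the SAP's difference and SDs, the same correlation in both arms and complete pre-op scores; relaxing either of the last two shrinks the gain. The sample size is not in error.

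**What to change.** In the SAP, make the primary analysis one linear model of PACU VAS on treatment and pre-op VAS, with heteroscedasticity-robust (for example HC3) standard errors. Alongside it:

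- Define pre-op VAS as the last value recorded before the study dose, since the schedule allows more than one day.
- Set a missing pre-op VAS to the overall mean, computed without regard to arm.
- Keep the unequal-variance t-test of the Power Analysis as a sensitivity analysis, and rule out a pooled t-test.
- Label the imbalance-triggered stratified analysis as supportive, or delete it, because the adjusted model takes over its purpose. Its effect on type I error cannot be judged, as the SAP does not say how it would be used.
- Bring the Protocol (Biostatistics, Analysis) into line. It defines the primary outcome as PACU VAS, but its sentence on the primary test names the quantity of opioid prescribed.

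The cost is wording in the two documents, with no new data collection. The risks are the loss of up to about one point of power if pre-op VAS is uninformative, and dependence on a missing rate that the documents do not give.

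### Does it matter that the SAP does not name the form of the primary t-test or say what its assumption checks lead to?

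*SAP*

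**What the plan says.** The SAP's analysis section commits, without condition, to a t-test on the VAS score: "an independent sample t-test will be conducted to assess if differences exist on VAS scores by the treatment group". The test is two-tailed at 0.05. Two checks are listed: "Normality of the scores will be assessed using the One-Sample Kolmogorov-Smirnov test" and "Homogeneity of variance will be assessed using Levene's Test for the Equality of Error Variances". No sentence attaches an action to either. The only conditional step for the primary outcome is a stratified analysis if patient characteristics are unbalanced, which is unrelated to these checks.

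The SAP's Power Analysis gives 59 per group for 80% power to detect a 1-unit difference, with SDs of 1 (from the pilot) and 2.5 (from literature), "using a two-sided two-sample unequal-variance t-test".

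The Protocol (Biostatistics, Analysis) defers to the later document: "A formal statistical analysis plan, crafted by the study team in partnership with the statistical consultants, will be finalized prior to data analysis". It also states "The primary outcome will be the score on the visual analog scale of pain in the PACU", yet a few lines later it says "For the primary outcome, student's t-test will be used to compare the amount of opioid prescribed".

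**The concern.** The term independent-samples t-test covers both the pooled and the Welch form. The sponsor's planning SDs differ 2.5-fold, so equal variances are not what the sponsor expects. If completers are unequal, the pooled form can be too liberal or too conservative.

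The normality check raises a second question. A bounded pain score with many low values may well fail it, and the plan does not say what then happens. If the primary test were picked after seeing the data, the nominal 5% would no longer hold.

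The Protocol adds to the doubt. It names Student's test and attaches it to the amount of opioid prescribed instead of the pain score.

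**Working it through.** **1. The plan's own sample size.** Inputs from the SAP's Power Analysis: difference 1, SDs 1 and 2.5, two-sided alpha 0.05, n = 59 per group.

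- Variance of the difference: 1²/59 + 2.5²/59 = 7.25/59 = 0.1229, so SE = 0.3505.
- Satterthwaite df: 0.1229² / [(1/59)²/58 + (6.25/59)²/58] = 76.1; critical value 1.992.
- Noncentrality: 1/0.3505 = 2.853. Noncentral t power = 80.4%.
- The same steps at n = 58 give df 74.8 and power 79.7%.

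So 59 is the smallest n that reaches 80%, and the figure reproduces. For the total, 118/(1 − 0.40) = 197, in line with about 200.

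**2. Pooled or Welch with equal completers.** With n per arm equal, the pooled SE is √[((1 + 6.25)/2) × (2/59)] = √(7.25/59), the same as the Welch SE. The t statistics are therefore identical, and only the reference df differ: 116 (critical value 1.981) against about 76 (1.992). Referring 1.981 to a t distribution with 76.1 df gives a two-sided error of 5.1%.

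**3. Chance differences in completers.** Simulated normal trials (1,000,000 per setting), 100 per arm, equal loss rates in both arms, SDs 1 and 2.5, equal means:

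| Loss rate | Pooled type I error | More favourable of the two forms |
|---|---|---|
| 5–10% (assumed) | 5.1% | 5.2% |
| 40–50% (SAP 40%, Protocol 50%) | 5.2% | 5.5–5.6% |

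If the drug has no effect at all, the two arms share one distribution and both forms hold 5.0%.

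**4. What a visible drift would need.** Take 60 completers in the SD-1 arm and 50 in the SD-2.5 arm (an assumed split).

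- True variance of the difference: 1/60 + 6.25/50 = 0.1417.
- Pooled estimate: [(59 × 1 + 49 × 6.25)/108] × (1/60 + 1/50) = 3.382 × 0.03667 = 0.1240.
- The pooled SE is too small by a factor √(0.1417/0.1240) = 1.069, and the error is 6.8%.
- The reverse split, 50/60, gives 3.7–3.8%.

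Both cases need unequal completion together with a drug that changes the variance but not the mean. The documents predict no differential dropout.

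**5. What the Levene check does in practice.** At SDs 1 and 2.5 with 59 per arm, Levene's test rejects in over 99.99% of simulated trials. The ordinary response is Welch, at about 5.0%.

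**6. The normality check.** Three score shapes on an assumed 0–10 scale (21% zeros; 30% zeros; right-skewed), same distribution in both arms, 59 per arm:

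| Quantity | Shape 1 | Shape 2 | Shape 3 |
|---|---|---|---|
| K-S rejects in at least one arm, critical value for estimated mean and SD | 95% | 99.8% | 99.8% |
| K-S rejects in at least one arm, standard table | 10% | 63% | 51% |
| Welch type I error | 5.0% | 5.0% | 5.0% |
| Better of Welch and Mann-Whitney, choice open in every trial | 6.0% | 6.0% | 6.8% |
| Better of the two, only when K-S (standard table) rejects | 5.5% | 5.8% | 6.2% |

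The planned t-test is valid in all three shapes even where the check rejects. The last two rows describe analysts who add a Mann-Whitney test and keep whichever p-value is smaller. Neither document mentions a rank test or a switch.

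**The case for a change.** The strongest argument for an edit is that the normality check will plausibly fail, that it must have been listed for a reason, and that a primary test should leave nothing to settle once data are seen. This needs neither unequal dropout nor an odd drug effect. Naming Welch outright would cost almost nothing: with equal variances it gives up 0.01 points of power at 59/59 and 0.11 at 70/48 against the pooled test.

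It is true that the text is incomplete and that one clause would make it tidier. But the SAP says without condition that a t-test will be done, so moving to a rank test would be a visible departure from the plan. The 6.0–6.8% range is an upper bound on that departure, under shapes and a scale that the documents do not give.

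A pre-set switch to Mann-Whitney would bring no clear gain either. It holds about 5% with the estimated-parameter critical value but 5.2–5.5% with the standard table. The power comparison depends on shape: Welch 83.1% against 74.1% for one skewed case, but 59.8% against 74.4% if the drug acts mainly by producing more zero scores.

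The Protocol sentence on opioid amount is a genuine inconsistency, but a separate one about which variable is tested. The same section, the Primary Endpoints section and the SAP all make the PACU pain score primary, and the Protocol defers to the SAP. It reads as a clerical slip and does not alter the primary comparison.

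**Conclusion.** No change follows. This is a missing detail that the SAP itself supplies: its Power Analysis names the unequal-variance test for the same VAS comparison, nothing in the SAP names a pooled test, and the Levene check leads to Welch at the planning SDs. Even if the pooled form were used, type I error would be 5.1% with equal completers and 5.2% with 40–50% loss at equal rates, and 59 per group stands at 80.4% power.

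This rests on 1:1 allocation, similar completion in the two arms and the planning SDs of 1 and 2.5. A markedly uneven split combined with a variance-only effect would take the pooled test to 6.8% or 3.8% in the 60/50 and 50/60 examples, but the documents give no reason to expect that. The normality figures rest on assumed score shapes and describe a departure from the plan.
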